#### Other Associated Risks

MRI: MRI scans are considered a safe way to noninvasively visualize tissue in adults and children. This study will be performed on a FDA approved scanner. There are no known significant risks or side effects associated with MRI procedures except the risk of metallic projectiles in the magnetic field or metallic objects in the body. Some participants report mild discomfort when undergoing magnetic resonance scans. Some participants have experienced claustrophobia (fear of enclosed spaces).

The major risk of having a research brain MRI is the identification of incidental findings, most of which turn out to be inconsequential. Nevertheless, being informed of a possible abnormality in a brain scan is anxiety provoking. In the largest pediatric brain imaging study to date, of 11,679 children ages 9-10 years-old, 17.2% had a finding that was judged to not require a referral, 3.7% had incidental findings for which referral was considered, and 20 (0.2%) were found to merit considering an immediate referral (99). The PI has nearly 30 years' experience in conducting pediatric neuroimaging studies and has always directly communicated any concerning findings to parents/guardians in a sensitive and forthright manner.

The MRI scanner also makes loud knocking or beeping sounds during imaging. Due to the rapid rate of change of the magnetic gradients during imaging, peripheral nerve stimulation is a possibility. If this happens, participants may feel creeping or tingling sensations, typically along their arms or lower back. Dizziness and nausea may occur if participants move their head rapidly in the bore of the magnet. Finally, there may be some heating from the radio frequency coils, the cables to the coils, and response and physiological monitoring devices. We do not use cables that can conduct electricity in the proximity of participants and have had no such untoward events in the past in over 15 years scanning young children.

Blood draw: This study involves blood draws, which may cause some discomfort, bruising, or transient pain at site of needle entry into the vein as with any blood draw. There is a slight risk of fainting. Infection can also occur at site where needle penetrates the skin.

Pregnancy-related risks: There are no data available on the risks associated with CBD use in pregnancy.

Burden of study time commitment: This proposal calls for participants and their caregivers to return to the clinic/attend virtual visits over WebEx regularly and participate in a relatively lengthy battery of assessments.

Mandated reporting of suspected child abuse or neglect: As mandated reporters, evidence of suspected child abuse or neglect would need to be reported to the appropriate authorities. This exception to confidentiality is explicitly provided in the consent document. If required, parents/guardians will be informed of the referral.

---

### 2.3.2 KNOWN POTENTIAL BENEFITS

It is possible that some study subjects will experience an improvement in their ASD and related symptoms while taking CBD during the study. For participants who experience benefit without significant side effects, parents/guardians may elect to continue CBD prescribed by their own physician. CBD is now available legally in New York State. It is also possible subjects may not benefit from being in this research study. Others with ASD may benefit in the future from what we learn in this study.

---

### 2.3.3 ASSESSMENT OF POTENTIAL RISKS AND BENEFITS

The common AE associated with CBD in previous research are typically mild (e.g., headaches, gastrointestinal symptoms), particularly when compared to the AE profile of currently approved medications for ASD. Nonetheless, all participants will be closely monitored for AEs during the treatment period and assessment of the need for discontinuation of treatment will be conducted as appropriate.

In regard to the potential for drug interaction effects, participants taking medications metabolized primarily by CYP2B6, CYP2C8, CYP2C9, CYP2C19, CYP3A4, or CYP2D6 isoenzymes will be excluded. Adverse effects related to the interaction between medications will be monitored, including tests of hepatic and hematological function at Baseline and at Weeks 6. Further, if a subject's baseline blood draw suggests borderline clinical abnormalities (that did not meet the cutoff for exclusion), they will be required to complete a Week 4 blood draw. Since transaminase elevations of greater than 3 times the upper level of normal (ULN) (plus elevated bilirubin levels) are significant predictors of severe liver injury and given that CBD can cause dose-related elevations in liver transaminases, potential participants with elevated baseline transaminase levels greater than 3 times the ULN plus elevations in bilirubin greater than 2 times the ULN, will be excluded from trial participation.

Further, while there are no data to suggest 9 mg/kg/day will be associated with increased risk, out of an abundance of caution, participants assigned to the highest dose (9 mg/kg/day) will be instructed to take half the dose (4.5 mg/kg/day, divided in two doses) per day for the first week of treatment before increasing to the full dose to minimize the chance for adverse events upon treatment initiation.

Lastly, if families are concerned about CBD showing up on a urine drug test, the study team will provide documentation that the subject is in a research study using a cannabis-related compound that has no psychoactive effects. Additionally, we will exclude participants with a history of cannabis usage or substance use disorders or a positive urine toxicological screen.

MRI scanning is optional. Participants who have no contraindications for MRI scanning and who agree to undergo MRI scanning and their parents/guardians, if they enter the scanning suite, will be carefully

screened for previous exposure to metallic fragments and for devices such as electrically, magnetically or mechanically activated implants, e.g., cardiac pacemakers, clips on blood vessels in their brain, or other metallic objects in their body, e.g., shrapnel, bullets, buckshot, or metal fragments. They will also be asked to leave all metallic and magnetic objects in their possession (e.g., keys, jewelry, credit cards) outside the magnet room. To manage the noise associated with the scan, earplugs are provided. Participants will also be instructed how to use an emergency handheld device to inform the operator if they feel discomfort, and/or wish to immediately stop scanning and be removed from the magnet. It is worth noting that the MRI scanning environment necessarily predicates the utmost concern for the complete comfort of the participant. We emphasize that even slight discomfort tends to result in participants moving during the scan, which degrades image quality. Therefore, prior to the imaging session, we have participants complete a mock scanner session using an MRI simulator, and also spend extra time when we place them on the gantry to make sure they are comfortable, and readjust as needed whenever they let us know that they are even slightly uncomfortable. For participants prone to fear of tight spaces (claustrophobia), special care will be taken during the mock scanner session to test if proceeding with training and the real MRI will be feasible for them. In general, once a participant has gotten over the novelty of entering the magnet bore, and has habituated to the knocking noises, the main issue is boredom, and staying awake for functional scans. Participants are asked to keep their eyes open during resting state scans to facilitate monitoring of wake status. Participants are free to sleep or watch a DVD or listen to music during several of the scanning sequences (e.g., structural scans). Given that we are using instruments that are calibrated to deliver energy levels judged to be well within safe limits, we expect no adverse events. Nonetheless, we will monitor all participants during scanning and be available for any follow-up that may be required.

In regard to AE associated with blood draws, the study team will offer EMLA cream to minimize discomfort, and precautions will be taken to prevent infection by using sterile technique.

Because risks of CBD use in pregnancy as well as MRI scanning in pregnancy are unknown, all potentially fertile subjects are required to use abstinence or a valid method of contraception to participate in the study. Menstruating females will undergo urine pregnancy test before initiation of study drug, as well as before each MRI scan. If a subject becomes pregnant during the study, she will immediately be discontinued from the medication. Subjects who become pregnant during the study, or within 30 days after completing the study, will be followed throughout the course of the pregnancy for safety, with the subject's permission and that of her parent/guardian. Information about the risks of the pregnancy and the possible effects on the fetus will be provided to support an informed decision in cooperation with the treating physician and the obstetrician. Any spontaneous abortion will be classified as a SAE.

Regarding the time commitment of participation, every effort has been made to reduce the time burden on participants and caregivers. A majority of the assessments are completed by the caregiver, and child assessments are kept to a minimum, with only diagnostic/screening measures completed at screening and a brief observational measure (~10-15 minutes) completed twice, at baseline and study completion at in-person visits. If virtual visits are conducted, the brief observational measure will not be administered and the diagnostic/screening measure will be conducted over WebEx. If needed, enrollment/baseline visits can be split into two visits. Caregivers may prefer to attend one of those visits (virtually or in-person) without their child to complete their measures. Caregivers will be encouraged to complete measures using secure electronic entry as much as possible. To give caregivers more flexibility, we will allow them the option to complete measures during the screening visit before the child has been confirmed eligible for the study or during the baseline visit. To improve

ease of scheduling, the participant will be given a window of time around the next visit date of +/-3 days. Reimbursement for time and travel will also be provided at each visit (\$75/each at the enrollment/baseline, 4-week and 6-week visits and \$40/each for the screening and 2-week visits; \$75 for each MRI scan; an additional \$10 will be provided on visits that include blood draws and brain MRIs [e.g., Screening Visit, Baseline Visit, Week-4 Visit, Week-6 Visit] to cover additional travel expenses). Of note, the time commitment and study burden are similar to those of other ASD treatment studies.

### 3 OBJECTIVES AND ENDPOINTS

OBJECTIVES	ENDPOINTS	JUSTIFICATION FOR ENDPOINTS
Primary		
Determine the optimal dose of CBD in children and adolescents with ASD	Establishment of optimal dose of CBD in children and adolescents with ASD, defined as the dose at which the greatest proportion of participants respond. Discussed further in the Dosing and Administration section, the definition of treatment response will be individualized for each participant based upon a predetermined target symptom cluster.	Identification of the optimal dose of CBD (within the range tested) is desirable given the insufficient research in this area and the potential for dose-dependent inverted-U effects (2, 9).
Secondary		
Identify the primary outcome measure for a subsequent double-blind placebo-controlled RCT	Change in core and associated symptoms from baseline based upon measures developed to assess ASD symptoms, symptoms often associated with ASD, and global functioning including: 
 
- ABC Social Withdrawal and Irritability Subscales
 
- ASC-ASD-Child and Parent
 
- AFEQ
 
- ADAMS
 
- BIS
 
- CGI-I
 
- CGI-S
 
- HSQ-ASD
 
- OSU Autism CGI Severity
 
- OSU Autism CGI Improvement
 
- RBS-R
 
- SCARED
 
- SDSC
 
- SRS-2
 
- SWAN (Part 2 of the trial)
 
- Vineland-3
 
	Measures were selected because they have been widely used in prior trials in ASD (ABC, CGI, HSQ-ASD, OSU Autism CGI, RBS-R, SCARED, SRS-2, SWAN [Part 2], Vineland-3), or have been used in a recent trial of CBD in Fragile X syndrome (ADAMS) or have been used in medication trials more broadly (SDSC), or represent new and innovative tools available in the ASD field (ASC-ASD; AFEQ; BIS).
Tertiary/Exploratory		
Assess underlying brain mechanisms using MRI	Change in brain activity, indexed by resting-state functional connectivity. Otherwise, results will be reported	Inform the feasibility of incorporating biomarkers (e.g., resting-state functional

OBJECTIVES	ENDPOINTS	JUSTIFICATION FOR ENDPOINTS
	qualitatively (conducted at in-person visits only, if participants agree)	connectivity) in our future studies and potentially yield testable hypotheses.

## 4 STUDY DESIGN

### 4.1 OVERALL DESIGN

The primary objective is to determine the optimal dose of CBD in children and adolescents with ASD; the hypothesis is that doseresponse curve may not be linear and that moderate doses of CBD may be therapeutically beneficial for core and associated symptoms in children and adolescents with ASD. The second objective of this study is to determine effect sizes for a variety of outcome measures, with the longer term goal of facilitating the selection of primary and secondary outcome measures for a subsequent placebo-controlled RCT. The third objective is to assess the feasibility of quantifying candidate biomarkers (e.g., resting-state functional connectivity) using MRI.

This single group single-site study will seek to enroll youth between the ages of 7 and 17 years who have a diagnosis of ASD with broadly average intelligence and who are fluently verbal. An adaptive design will be employed to allow for evaluation of optimal dosing while collecting data on core and associated ASD symptoms and any Aes that may present. Under the adaptive design algorithm we implemented, we ended recruitment after enrolling 15 participants and testing two doses. Given the higher rate of response on the higher of the two doses tested (44% vs. 16%), and the suggestion that higher doses of CBD may particularly target dopamine type 2 high affinity receptors (D2Rhigh) in the striatum, we have modified the study by implementing part 2 (described further on page 17-20), to recruit up to 15 youth (within the previously approved total accrual of 30 who would enroll) with clinical profiles that most closely resemble youth classified as responders in Part 1 of the trial.

It is important to note that all endpoints in this study are exploratory; the research base is too limited to make confident predictions. Nonetheless, given the lack of alternative pharmacological options, the benign AE profile, and the potential for CBD to fill this treatment gap, this line of work is necessary to direct future research in the field.

### 4.2 SCIENTIFIC RATIONALE FOR STUDY DESIGN

Suggested dosing to address psychiatric symptoms may be substantially lower compared to dosing in epilepsy studies, which has been the focus of most pediatric CBD research. Further, previous research suggests that CBD has dose-dependent effects on social behavior and anxiety. Therefore, prior to conducting a double-blind trial, identifying optimal dosage is imperative. The BOIN design was employed as our dose finding approach. The BOIN design is flexible and sensitive to nonlinearity, and enables the designation of an optimal dose level based upon the proportion of participants who respond to the treatment.

The BOIN design allowed us to test the intermediate dose (n=9) and the low dose (n=6) and to observe a non-significantly higher rate of response (44%) on the intermediate dose than on the low dose (16%). Based on the overall excellent safety profile in part 1 (all participants completed treatment without any

severe adverse events or need to discontinue treatment) and the suggestion that higher doses of CBD may particularly target striatal D2Rhigh receptors, we have modified the second part of the trial to administer only the still untested 9 mg/kg/day dose, and to focus on participants who present with both ASD and ADHD, as they appear to be the ones most likely to be classified as responders in part 1. This is described in further detail on pages 17-20.

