### 5 STUDY POPULATION

#### 5.1 INCLUSION CRITERIA

Patients who will be selected for this study will meet the following criteria:

- Male or female pediatric outpatients aged between and including 7 to 17.9 years old
- Diagnosis of ASD confirmed by the ADOS-2 or CARS-2-HF and DSM-5 criteria

- Part 2: Diagnosis of ADHD confirmed by clinician review of the K-SADS-COMP
- SRS-2 Total T-score of 66 or higher
- CGI-S score of 4 or higher
- Physical exam and laboratory results that are within normal range for their age
- Fluent speech
- Estimated IQ of at least 80
- Presence of a parent/legal guardian who is able to consent for their participation and complete assessments regarding the child's development and behavior throughout the study
  - Child Assent will be obtained.

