    - Non-response: no-to-minimal therapeutic benefit captured by a CGI-I score of 3 (minimally improved) or greater (i.e., no change or any worsening) determined by consensus as indicated above, and/or severe AE, defined as severe cognitive or behavioral toxicity, impaired liver and renal function, or impaired hematopoiesis that is deemed to be potentially or likely related to study medication (also see section 8.3.2), causing early discontinuation of study intervention.

While applying a uniform statistically derived algorithm for defining treatment response and non-response for all patients would have been preferable, the above procedures were implemented given the exploratory nature of the study and the wide range of therapeutic effects that CBD may exert. The intent of this exploratory study has been to provide the foundation for a well-defined subsequent RCT.

Over the first 15 participants, we have identified five as responders, for an overall response rate of 33%, and a response rate of  $4/9 = 44\%$  on 6 mg/kg/day, as opposed to the 60% rate anticipated on the optimal dose. The response rate on 3 mg/kg/day was  $1/6 = 16\%$ . Per the BOIN design that we implemented, we have excluded both the 6 mg/kg/day and 3 mg/kg/day dose for further testing. We believe that it would be scientifically valuable to test the 9 mg/kg/day dose on the remaining 15 participants that were originally approved for this open trial. The purpose would be to further confirm the overall safety of the AE profile – which is likely given the pediatric experience with 10 mg/kg/day and 20 mg/kg/day in patients with refractory epilepsy who are more medically fragile. It has also been hypothesized that higher doses of CBD may have preferential effects on D2high receptors in the striatum. If so, that might explain why all five responders had ASD, as well as ADHD.

Accordingly, we now request that we amend the open trial to test only the dose of 9 mg/kg/day and that we require the combination of ASD and ADHD for inclusion. All other aspects of the trial would be unchanged, other than adding the Strengths and Weaknesses of Attention-Deficit/Hyperactivity Disorder Symptoms and Normal Behavior (SWAN) as a dimensional measure of ADHD and completing the K-SADS-COMP at the screening visit rather than the baseline/enrollment visit so that the study clinicians can confirm the presence of an ADHD diagnosis.

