Given our experience with the first 15 participants, we anticipate that at least 1/3 will be classified as responders. If none of the first 6 participants on 9 mg/kg/day are responders, then we would eliminate the dose and terminate the trial. A low, non-zero response rate, as shown below in Table 3, would also determine terminating the trial, as it would be tantamount to evidence that the optimal dose was 6 mg/kg/day, our initial starting dose.

**Table 3.** Dose elimination rules for cohorts 6 to 10

Cohort	1	2	3	4	5	6	7	8	9	10
Number of participants to be treated at the current dose	3	6	9	12	15	18	21	24	27	30
Dose administered (mg/kg/d)	6	6	3	3	6	9	9	9	9	9
Cumulative N of respondents	1	3	4	4	5	-	-	-	-	-
Terminate if # of responses <=						NA	5	6	7	

Thus, we propose to enroll at least six more participants on the dose of 9 mg/kg/day. If none of them respond, the cumulative number of respondents would remain 5, and we will discontinue the trial; if at least 1 responds within the first 6, we will enroll 3 additional participants. If the total number of responders remains 6, we will discontinue the trial. If the number of responders is 7 or more after 9 participants are enrolled, we will enroll an additional 3 participants for a total of 12 on this dose. If the number of responders does not increase beyond a total of 7, we will terminate due to likely futility.

Table 4 provides the operating characteristics of this design extension for a variety of true response rates.

**Table 4.** Operating characteristics of 9 mg/kg/day evaluation

	Dose 1	Dose 2	Dose 3	Dose 4	Dose 5
True response rate	0.1	0.2	0.3	0.4	0.5
Probability of early termination(%)	90.4	60.8	31.0	11.9	3.5

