### 9.3 POPULATIONS FOR ANALYSES

Participants included within the analysis datasets include all participants in the trial, including both responders and non-responders, to examine efficacy at varying doses as well as safety and tolerability across the whole sample.

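### The 9 mg/kg/day result will come only from youth with ASD plus ADHD, but the plan does not stop it being used to choose one optimal dose for ASD as a whole

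*Combined protocol and SAP*

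**What the plan says.** Section 5.1 adds one criterion for the second part only: "Part 2: Diagnosis of ADHD confirmed by clinician review of the K-SADS-COMP". Section 4.2 explains that the aim is to "focus on participants who present with both ASD and ADHD, as they appear to be the ones most likely to be classified as responders", and 6.1.2 offers a receptor hypothesis that might explain "why all five responders had ASD, as well as ADHD". Part 2 tests 9 mg/kg/day and no other dose.

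Part 1 had no ADHD criterion. Its results (4.2 and 6.1.2) are 1 responder of 6 at 3 mg/kg/day and 4 of 9 at 6 mg/kg/day.

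The primary endpoint in Section 3 is "Establishment of optimal dose of CBD in children and adolescents with ASD, defined as the dose at which the greatest proportion of participants respond". Section 9.4.1 makes the selection by isotonic regression once the trial is complete. Section 9.4.2 takes the dose whose isotonic estimate lies nearest the target, which is 0.60. Section 9.3 reads "Participants included within the analysis datasets include all participants in the trial". Section 9.4.7 plans no subgroup analysis. For Part 2, 9.4.2 refers the reader to Tables 3 and 4, which hold a stopping rule and its operating characteristics.

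ADHD status in Part 1 should already be on file. Section 8.1 uses the K-SADS-COMP to characterise the sample, and the Part 2 change described in 6.1.2 is one of timing: "completing the K-SADS-COMP at the screening visit rather than the baseline/enrollment visit".

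**The concern.** No one enrolled under the ADHD requirement receives 3 or 6 mg/kg/day, and no one receives 9 mg/kg/day without it. A 9 mg/kg/day rate above or below 44% could therefore reflect the dose, the restriction, or both. Nothing in the plan separates them: there is no ADHD-matched comparison, and no statement limits the conclusion to ASD plus ADHD.

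The primary objective is at stake. Section 4.2 treats finding the dose as essential before a double-blind trial, so the selected dose is meant to be carried forward. If 9.4.2 is applied across both parts, the report would name a dose for ASD in general when one of the three doses was studied only in a subgroup picked for its expected response.

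**Working it through.** **Inputs.** Part 1 results 1/6 and 4/9 (6.1.2); all five responders had ADHD (6.1.2); target 0.60 (6.1.2, 9.4.2); stops on 9 mg/kg/day at 0/6, at most 1/9 and at most 2/12. The stops follow from the text around Table 3 after subtracting the five Part 1 responders from the cumulative totals of 5, 6 and 7.

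**Reproducing Table 4.** With true rate p, the three looks give

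P(stop) = (1−p)^6 + 6p(1−p)^8 + 33p²(1−p)^10.

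At p = 0.1 this is 0.531 + 0.258 + 0.115 = 0.905. Over p = 0.1 to 0.5 it gives 90.5, 60.5, 30.5, 11.9 and 3.5%, against 90.4, 60.8, 31.0, 11.9 and 3.5% in Table 4. The stopping rule is read correctly.

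**Matched comparator.** All four responders at 6 mg/kg/day had ADHD. If m of the nine had ADHD, the ADHD-only rate is 4/m. The plan does not give m, so it is assumed: m = 9, 8, 7, 6 gives 44, 50, 57, 67%.

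**No dose difference.** Let 9 mg/kg/day have true rate 4/m, apply the stops, and let X be responders of 15. A stopped trial counts as not exceeding and not selected.

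- Exceeding the unrestricted 44% needs X ≥ 7 (7/15 = 46.7%).
- Exceeding the matched rate needs X ≥ 7, 8, 9 or 11 for m = 9, 8, 7, 6. At m = 6, X = 10 is an exact tie (10/15 = 4/6).

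**Selection under 9.4.2.** Assumptions: isotonic regression weighted by n; the Part 1 doses excluded from further testing remain selectable; 3 mg/kg/day is left out of the matched comparison.

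- Mixed comparator (1/6, 4/9, X/15): 9 mg/kg/day is selected for X = 3 to 11. For X = 3 to 6 the two upper doses pool below target and the tie rule takes the higher. At X = 11 the distances are |0.733 − 0.60| = 0.133 and |0.444 − 0.60| = 0.156; at X = 12 the first becomes 0.200.
- Matched comparator (4/m, X/15): selected for X = 3 to 10 at m = 8 (0.067 against 0.100 at X = 10), X = 3 to 9 at m = 7 (0.000 against 0.029 at X = 9), and X = 3 to 8 at m = 6 (pooled 12/21 = 0.571 at X = 8; pooled 13/21 = 0.619 at X = 9, where the tie goes to the lower dose).

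| m (assumed) | Matched rate | 9 mg/kg/day exceeds 44% | Exceeds matched rate | Selected, mixed | Selected, matched |
|---|---|---|---|---|---|
| 9 | 44% | 53% | 53% | 92% | 92% |
| 8 | 50% | 70% | 50% | 95% | 90% |
| 7 | 57% | 86% | 52% | 93% | 67% |
| 6 | 67% | 97% | 40% (plus 21% ties) | 79% | 20% |

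**Is ADHD a predictor at all?** If K of the 15 had ADHD and it were unrelated to response, all five responders would have it with probability C(K,5)/C(15,5). For K = 8, 12 and 14 this is 56/3003 = 2%, 792/3003 = 26% and 2002/3003 = 67%. K is not given.

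**Precision.** Exact 95% intervals: 4/9, 14 to 79%; 4/6, 22 to 96%; 1/6, 0.4 to 64%.

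**The case against.** The enrichment is deliberate and disclosed in several sections, and 4.1 says "all endpoints in this study are exploratory; the research base is too limited to make confident predictions". Part 2 can also be read as a stand-alone evaluation. Section 6.1.2 drops both Part 1 doses from further testing and gives safety confirmation as a purpose, Table 5 is labelled as Part 1, and 9.4.2 refers Part 2 to Tables 3 and 4. Section 9.3 defines a dataset and does not itself prescribe a pooled dose comparison. Section 9.4.7 does not forbid a descriptive table.

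Much of this stands. A reader might infer that the plan definitely pools the two parts and that its answer is biased; the text supports neither as fact. The confounding is conditional on how 9.4.2 is applied, and its size cannot be worked out from the documents. What does not stand is that disclosure or the exploratory label cures it. Tables 3 and 4 contain no selection rule, 9.4.1 still places selection after the whole trial, and Section 3 still names ASD.

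A reader might also fault 6.1.2 for saying of a low 9 mg/kg/day rate that "it would be tantamount to evidence that the optimal dose was 6 mg/kg/day". That criticism is weak. Termination needs at most 2/12 (17%) in the group thought likeliest to respond, and if ADHD raises response, so low a rate counts more strongly against 9 mg/kg/day. No change is asked there.

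**Conclusion.** The mismatch between the population given 9 mg/kg/day and the population named in the endpoint is established from the text. So is the lack of clarity over whether 9.4.2 covers 9 mg/kg/day. A biased result is not established.

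If the selection spans both parts, the distortion at 6 mg/kg/day ranges from none (all nine had ADHD) to the illustrated size: with 8, 7 or 6 of nine, 9 mg/kg/day is selected in 95, 93 or 79% of trials against the mixed comparator and 90, 67 or 20% against the matched one. In these scenarios the mixing favours 9 mg/kg/day. The fall from 95 to 79% might be taken to mean that the effect reverses. It does not: the fall comes from the nearest-to-0.60 rule as the true rate rises, and the matched figure is lower in each of the three.

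The illustration treats tiny subgroup rates as true and assumes no dose difference within ASD plus ADHD. The premise that ADHD predicts response is post hoc and could be chance if most of Part 1 had ADHD.

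**What to change.** 1. State whether 9.4.2 applies to 9 mg/kg/day, or whether Part 2 is a stand-alone futility evaluation.
2. Limit the 9 mg/kg/day result to youth with ASD plus ADHD, and do not declare an optimal dose for ASD as a whole from the unrestricted comparison across parts.
3. Tabulate Part 1 response at each dose by K-SADS-COMP ADHD status, with exact intervals, beside the all-participant rates. Say whether ADHD was ascertained as in Part 2. Make any comparison with 9 mg/kg/day descriptively within ASD plus ADHD, labelled post hoc. If that subset is too small, report 9 mg/kg/day alone with its exact interval.
4. Date the change and disclose what had been seen. The Summary of Changes cites preliminary analyses with n=19; Part 1 had 15 participants, so 19 − 15 = 4 or more may be from Part 2.

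The cost is wording in the synopsis and in Sections 3, 4.1, 9.3, 9.4.1, 9.4.2 and 9.4.7, plus one table from data that should already be held. No participants or visits are added. The downsides are small Part 1 denominators, wide intervals, Part 1 subset rates inflated by post hoc selection, and a narrower conclusion.
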